11. STATISTICAL CONSIDERATIONS

a. General considerations

The statistical analysis plan will be developed and finalized before database lock.

Descriptive statistics will be obtained for all variables: mean, median, standard deviation and range, Q1, Q3, and CI 95% for continuous variables, and frequencies and percentages for categorical variables.

Summary statistics will be provided by treatment groups for disposition, demographics, baseline characteristics, exposure to investigational product, adverse events, concomitant medication, labs and clinical outcome assessment data.

A Chi- square test or Fisher test if applicable will be used to compare categorical variables between groups. Time-to-event variables will be estimated by the Kaplan-Meier method from the randomisation. The log-rank test will be used to compare the survival curves. All the other endpoints will be compared between the two arms with appropriate statistical tests. All statistical tests will be two-sided with an α -level of 0.05.

b. Sample size

The primary endpoint of this study is the 6mSROT-50 (≥50x10⁹/L) rate at 6 months from treatment cessation. In patients with newly diagnosed primary immune thrombocytopenia

^b Listing for reconciliation should include all ICSRs submitted to Amgen Safety per contract (for studies in Table 2 listing should contain SUSARs, pregnancy and lactation exposure (and any associated reports/outcomes), USADEs, SADEs and non-serious ADEs).

treated with dexamethasone 40 daily x 4 days for one to three cycles, 6mSROT-50 (≥50x10⁹/L) at 6 months from treatment cessation has been assumed to be 30% [2]. The sample size was based on the assumption that ROM + DEX can improve sustained response at 6 months from treatment cessation up to 56.6% similarly to eltrombopag plus dexamethasone as described by Zhang [2]. A total of 63 patients/arm are required to achieve 80% power to detect a difference with a two-sided significance level of 5%, if the true 6mSROT-50 rates at 6 months from treatment cessation are 30% in the DEX arm and 56,6% in the ROM + DEX arm and assuming a dropout rate of 15%. The total minimal size is 126 patients to be randomized.

c. Analytical Populations

Safety Population

The safety population will consist of all randomized subjects who received at least one dose of study treatment. Subjects will be analysed according to the treatment actually received. Analysis for safety endpoints will use this analysis set.

ITT Population

All patients who are randomized will be included in the ITT Population. The ITT Population will be used to summarize subject disposition and baseline characteristics. Patients will be analysed according to the treatment they were allocated to at randomization; not necessarily the treatment they actually received. Results will be presented "as randomized."

mITT Population

All patients who are randomized and received at least one dose of study medication will be included in the mITT Population. The mITT Population is the primary analysis population for efficacy. Patients will be analysed according to the treatment they were allocated to at randomization; not necessarily the treatment they actually received. Results will be presented "as randomized."

rITT Population

All patients who are randomized and received at least one dose of study medication and achieved response (R) at any time during the study will be included in the rITT Population. The rITT Population will be used for the analysis of time to loss of response. Patients will be analysed according to the treatment they were allocated to at randomization; not necessarily the treatment they actually received. Results will be presented "as randomized."

d. Analysis of Primary Objective

The primary endpoint is 6mSROT-50 rate at 6 months (180 days) from treatment cessation.

The proportion of patients with 6mSROT-50 and corresponding 95% CIs for each study arm will be provided. A Chi-square test or Fisher test if applicable, will be used to compare the proportion of 6mSROT-50 between treatment arms.

e. Analysis of Secondary Objectives

i. Secondary Efficacy evaluations

For the analysis of the secondary endpoints, following analyses will be conducted:

- The proportion of patients with 6mSROT-30, 12mSROT-30 and 12mSROT-50 and corresponding 95% CIs for each study arm will be provided. A Chi-square test or Fisher test if applicable will be used to compare the proportion of each endpoint between treatment arms.
- The proportion of patients with CR, R, GR or TR at 6 and 12 and End of study Visit (visit 12 months after the last dose of study treatment) will be calculated and corresponding 95% CIs for each study arm will be provided. A Chi-square test or Fisher test if applicable will be used to compare the proportion of each endpoint between treatment arms.
- To compare the time to first response (R) in both arms, Kaplan-Meier method will be used. Patients who not achieve R will be censored at the date of the last followup. Median and 95% CI, number of events and censored and risk number of patients will be provided. Log rank test will be used to compare time to first response between treatment arms. We will evaluate this in the total sample and in the absence of any rescue treatment.
- The proportion of patients with ER at Day 7 and IR at Day 30 from randomisation will be calculated and corresponding 95% CIs for each study arm will be provided.
 A Chi- square test or Fisher test if applicable will be used to compare the proportion of each endpoint between treatment arms.
- Descriptive statistics (mean, median, standard deviation, min, max, Q1 and Q3) and Student's t test will be used to compare the duration of platelet response through the following endpoints:
 - maximum number of consecutive days with platelet response (CR, R, GR and TR) along the study period and,
 - total number of days with platelet response (CR, R, GR and TR) along the study period in both arms. We will evaluate them in the total sample and in the absence of any rescue treatment.
- To compare the time to loss of response (LoR) in the subgroup of patients who achieve R (rITT population) between both arms, Kaplan-Meier method will be used. Patients who do not achieve LoR will be censored at the date of the last follow-up. Median and 95% CI, number of events and censored and risk number of patients will be provided. Log rank test will be used to compare time to first response between treatment arms.

 The proportion of patients requiring any rescue treatment along the study period will be calculated and corresponding 95% CIs for each study arm will be provided.
 A Chi-square test or Fisher test if applicable, will be used to compare the proportion between treatment arms.

Frequency and proportion of patients with adverse events, including bleeding events measured by the WHO bleeding scale will be provided. A Chi-square test or Fisher test if applicable will be used to compare the proportion between treatment arms.

- Quality of life measures using the SF-36 v2, FACIT-F and ITP-PAQ will be analysed. Change from baseline Day 1, (the day of administration of the first dose of study medication) to Week 8, Month6 (Day 180), Month12 (Day 365) and End of study Visit (visit 12 months after the last dose of study treatment) of SF-36 v2, FACIT-F and ITP-PAQ total score and each dimension score of SF-36 v2, FACIT-F and ITP-PAQ will be calculated. Both the change of scores and the scores at every assessed time point will be reported using the mean, median, standard deviation, min, max, Q1 and Q3.Student's t test will be used to compare the scores between treatment arms at different time points. Paired Student's t test will be used to evaluate the change from baseline at different time points within each treatment arm.
- The sum of all worst grades within each domain from the ITP-BAT questionnaire will be calculated and described at every assessed time point using the mean, median, standard deviation, min, max, Q1 and Q3.Student's t test will be used to compare the scores between treatment arms at different time points. Also, the change from baseline to Day 1, Week 8, Week 12, Month6 (Day 180), Month12 (Day 365) and End of study Visit (visit 12 months after the last dose of study treatment) of the sum of all worst grades within each domain from the ITP-BAT questionnaire will be calculated and described at every assessed time point using the mean, median, standard deviation, min, max, Q1 and Q3. Paired Student's t test will be used to evaluate the change from baseline at different time points within each treatment arm.
- Health resources use (HRU) associated with the ITP from treatment initiation (outpatient visits and home health care, hospitalizations and emergency visits, diagnostic procedures, pharmacological and non-pharmacological treatments and HRU related to of adverse drug reactions) and loss of productivity (number of days of absenteeism from school or work) will be summed up along the study and described using the mean, median, standard deviation, min, max, Q1 and Q3. Student's t test will be used to compare the scores between treatments.

In all hypothesis testing, p<0.05 will be considered statistically significant. No adjustments for multiplicity will be done. Since the amount of analysis of secondary objectives is numerous, results of the secondary endpoints should be considered exploratory and interpreted with caution.

ii. Secondary Safety evaluations

Safety assessment will consist of monitoring adverse events (AEs), including serious adverse events (SAEs) and laboratory safety parameters. AEs will be graded according to National Cancer Institute Common Terminology Criteria for Adverse Events (CTCAE) version 5.0. Bleeding events will be carefully monitored. AE terms will be coded using MedDRA (lastest version). The description of number and percentage of patients with each adverse event ordered by SOC/PT by grade and total will be summarized descriptively by treatment group.

The number of patients experiencing AEs and number of AEs will be summarized by treatment group using frequency counts.

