The risks are those inherent in the usual treatment of ITP, the benefit is the earlier access to the use of thrombopoietin analogues, reducing the long-term side effects of steroids, which have been shown to be greater than those of steroids. In addition, the potential benefit is that the early combination of two types of ITP treatment that act via different pathways may improve ITP treatment outcomes by reducing the rate of chronicity, which with steroid monotherapy is 60% at 6 months post-treatment cessation

iv. Romiplostim

The indications for romiplostim have recently been updated. Romiplostim is indicated for the treatment of primary immune thrombocytopenia (ITP) in adult patients who are refractory to other treatments (e.g., corticosteroids, immunoglobulins).

Romiplostim is a peptibody that includes a carrier domain (IgG1 Fc portion) and a peptide-containing domain (four peptides, each comprising 14 amino acids, designed to activate the TPO receptor [c-mpl; TPO-R] but avoid production of antibodies that can bind to endogenous TPO) [21–23] due to romiplostim has no amino acid sequence homology to endogenous TPO (eTPO). The peptides bind to the extracytoplasmic domain of the TPO-R and activate the receptor similarly to that of endogenous TPO, meaning that romiplostim and endogenous TPO compete for receptor binding [22,23].

For a complete summary of safety and efficacy data collected for the romiplostim clinical development program, please refer to the most recent version of the Investigator's Brochure.

Clinical efficacy and safety

In clinical trials, treatment with romiplostim resulted in dose-dependent increases in platelet count. Time to reach the maximum effect on platelet count is approximately 10-14 days, and is independent of the dose. After a single subcutaneous dose of 1 to 10 mcg/kg romiplostim in ITP patients, the peak platelet count was 1.3 to 14.9 times greater than the baseline platelet count over a 2 to 3 weeks period and the response was variable among patients. The platelet counts of ITP patients who received6 weekly doses of 1 or 3 mcg/kg of romiplostim were within the range of 50 to 450x10⁹/L for most patients.

Results from pivotal placebo-controlled studies

The safety and efficacy of romiplostim was evaluated in two placebo-controlled, double-blind studies in adults with ITP who had completed at least one treatment

prior to study entry and are representative of the entire spectrum of such ITP patients.

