To evaluate efficacy of three-period pulses of high-dose dexamethasone, adult naïve ITP patients for 3 months from diagnosis with a count of platelet <30×10⁹/L or more than 30×10⁹/L with the signs of bleeding existence based on bleeding grading scores were included were randomly assigned to receive prednisone or three-pulse regimen of high-dose dexamethasone. dexamethasone group, 40 mg of dexamethasone was administered for 4 consecutive days and was repeated in 14-day intervals for three pulses of treatment. Patients in the prednisone group received 1.0 mg/kg of prednisone orally per day for 4 consecutive weeks. The initial response rate of platelet count in the high-dose dexamethasone group was significantly higher than the prednisone group. The initial and sustained response (SR) rate of platelet count in the high-dose dexamethasone group was significantly higher. In fact, in the high-dose dexamethasone group, more patients reached SR after the 8-month follow-up. These results suggest that a three-pulse high-dose dexamethasone regimen could be better to achieve the SR and overall response without the burden of long-term corticosteroid consumption and concludes that in patients with ITP who have not received any kind of treatment, high-dose dexamethasone was more effective than conventional prednisone therapy [30].

On the other hand, a systematic review and meta-analysis of randomized controlled trials using dexamethasone or prednisolone showed a higher incidence of sustained response favourable to dexamethasone when used more than one course of dexamethasone or tapering corticosteroids. The overall response at day 28 was also significantly improved with dexamethasone. In addition, there were also significantly fewer adverse events in the dexamethasone arm and the study concluded that use of dexamethasone instead of prednisolone may be more beneficial as the initial therapy for ITP patients [31].

vi. Dexamethasone plus eltrombopag

Another study [2] compared dexamethasone alone vs a regimen of eltrombopag plus pulsed dexamethasone as first-line therapy. Sustained response off therapy was defined as maintaining platelet counts >50x10⁹/L for more than six months without further ITP therapy. 56.6% patients achieved the primary endpoint and this was statistically superior that the assumed response rate of 30% with dexamethasone alone.

b. Study rationale

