Primary immune thrombocytopenia (ITP) is a disease that results from autoimmune destruction of platelets and suppression of platelet production[32]. Newly diagnosed ITP is considered as lasting up to 3 months, followed by persistent (3-12 months) and chronic disease (12 months) [33]. Frontline therapy includes corticosteroids and intravenous immunoglobulin (IVIg). Prednisone at a dose of 1 to 2 mg/kg raises platelet count in 70% to 80% of patients; however, only a small portion achieves a sustained remission [12]. High-dose dexamethasone is initially effective in 85% of patients. Nevertheless, 50% relapse within the first 6 months [33-35]. Despite corticosteroids remain the standard of care, the high failure/relapse rates and considerable adverse effects from long-term use stimulates the search for better treatments [12,35,36]. Sustained response (SR) rates ranging from 58 to 78% using rituximab plus dexamethasone as frontline therapy have been reported [37-41]. There is little experience regarding the use of thrombopoietin analogues as first line treatment. Gómez-Almaguer et al [42] described a 66.7% of relapse free survival after 12 months of absence of eltrombopag treatment in patients with newly diagnosed ITP.

This study aims to evaluate dexamethasone and romiplostim combination as first line treatment in newly ITP patients to improve SROT avoiding bleeding, corticosteroids toxicity and necessity of rescue treatments.

c. Study objectives

Primary objective:

To evaluate the superiority of romiplostim plus dexamethasone vs dexamethasone alone after 6 months (≥180 days) from treatment cessation in patients with newly primary immune thrombocytopenia (ITP) in terms of sustained

response off any ITP treatment (6mSROT-50) and without WHO grade 2 or more bleeding.

Maximum time on treatment with romiplostim will be 12 months (365 days). Then, patients will be followed up for 6 additional months (180 days) after stopping romiplostim.

Secondary objectives:

- To evaluate the superiority of romiplostim plus dexamethasone vs dexamethasone alone after 6 months (≥180 days) from treatment cessation in patients with newly primary immune thrombocytopenia in terms of sustained response off any ITP treatment (6mSROT-30) from treatment cessation and without WHO grade 2 or more bleeding.

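### The primary efficacy set leaves out randomised patients who were never dosed in an open-label trial, and the stated 80% power treats 15% dropouts as removed although that set keeps every dosed patient

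*Protocol*

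**What the plan says.** Protocol section 11.c defines the mITT set as randomised patients with at least one dose, analysed in the arm allocated, and then states: "The mITT Population is the primary analysis population for efficacy". The all-randomised set has a narrower job: "The ITT Population will be used to summarize subject disposition and baseline characteristics". No efficacy analysis on all randomised patients is named. Section 7.d says that blinding does not apply because the study is open label.

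Section 11.b gives the size: "A total of 63 patients/arm are required to achieve 80% power", at a two-sided 5% level, with 6mSROT-50 rates of 30% (DEX) and 56.6% (ROM + DEX) and 15% dropout, for a total of 126. The section does not say whether the two rates refer to patients who complete the off-treatment window or to everyone randomised.

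The primary endpoint (section 6.b) needs at least 180 consecutive days from treatment cessation with platelets at or above 50x10⁹/L, no ITP or rescue treatment, and no WHO grade 2 or higher bleeding.

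**The concern.** There are two separate issues, both in section 11.

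The first is the analysis set. Patient and site know the arm before the first dose, and the arms differ in burden: weekly injections for up to 12 months against up to three four-day steroid courses. Refusing to start can therefore depend on allocation. Dropping those patients gives up part of the protection of randomisation in the one comparison that carries the trial.

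The second is the power statement. It is built as though dropouts disappear from the analysis, yet the chosen set retains anyone who took a dose. A retained patient whose 180-day window was never documented has to be classified somehow. Counting such patients as not achieved is the natural reading of the endpoint, and it dilutes both rates. The power of the planned analysis may then differ from the stated figure, which matters most when a non-significant result has to be interpreted.

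**Working it through.** **Inputs (section 11.b):** p1 = 0.30, p2 = 0.566, difference 0.266, two-sided alpha 0.05 (z = 1.96), power 80% (z = 0.8416), dropout 15%, 63 per arm, 1:1 allocation.

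**1. Reproducing the plan's figure.** Pooled-variance formula, mean rate (0.30 + 0.566)/2 = 0.433:

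n = [1.96·√(2·0.433·0.567) + 0.8416·√(0.30·0.70 + 0.566·0.434)]² / 0.266²
= (1.3734 + 0.5681)² / 0.0708 = 53.27 evaluable per arm.

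53.27/0.85 = 62.7, which rounds up to 63. The stated size is reproduced, and there is no arithmetic error in it.

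**2. What the 80% depends on.** Power = Φ{[0.266·√n − 1.3734] / √(0.30·0.70 + 0.566·0.434)}:

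- n = 63 × 0.85 = 53.55 per arm: 80.2%
- n = 63 per arm, rates unchanged: 86.3%

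So 80% corresponds to 15% of patients leaving the denominator.

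**3. Keeping all 63 per arm.** Let L be the share of would-be achievers lost because their window is not documented. L is taken as equal in both arms, and both rates are multiplied by (1 − L):

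| L | DEX | ROM + DEX | Power at 63 per arm |
|---|---|---|---|
| 0% | 30.0% | 56.6% | 86.3% |
| 5% | 28.5% | 53.8% | 83.0% |
| 9% | 27.3% | 51.5% | 80.1% |
| 15% | 25.5% | 48.1% | 75.5% |

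In the last row, exact enumeration of the chi-square test gives 76.5%. Restoring 80% at those rates would take 70.2, that is 71 per arm (142 in total).

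The first row is also the answer if 30% and 56.6% already count dropouts as failures. The last row applies if they are completer rates and all 15% become non-achievers independently of outcome.

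**4. The analysis set.** No calculation is possible. mITT removes only never-dosed patients, and the protocol gives no expected number of them. The figures in steps 2 and 3 concern dropout and do not measure the effect of choosing mITT.

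**The case against.** **On the analysis set.** Few never-dosed patients are to be expected. Randomisation is scheduled at the Day 1 visit, both arms start with the same four days of oral dexamethasone, and mITT patients are analysed as randomised. This makes a large bias unlikely. It does not justify the exclusion, because an all-randomised primary analysis costs nothing and removes the question.

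**On power.** Inflating for dropout is conventional, and the classification of dropouts may be left to the analysis plan. The 75.5% is also the low end of a range. Section 8.b lists treatment failure among the reasons for removal from the study, and such patients are already non-achievers in the assumed rates, so multiplying by 0.85 partly counts them twice. DEX patients finish treatment early and can complete their window before a late dropout. These points stand: about 76% is conditional, and the range in step 3 straddles 80%. What remains is that section 11.b does not say which kind of rate it uses, and its 80% matches a denominator that the stated set does not have.

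**A stronger reading that the text does not support.** A reader might infer that power is far lower at a control rate the protocol itself gives. Section 5.a.iii speaks of benefit "by reducing the rate of chronicity, which with steroid monotherapy is 60% at 6 months post-treatment cessation", which suggests 40% not chronic. Section 5.b says that high-dose dexamethasone is initially effective in 85% and that "50% relapse within the first 6 months", which suggests 0.85 × 0.50 = 42.5%. Against 56.6% with 53 evaluable per arm, power would be 40% and 30%. But neither figure is a 6mSROT-50 rate. No platelet threshold is attached to either, and the primary endpoint adds conditions on treatment and bleeding, so 30% does not contradict them. The only 6mSROT-50 control rate stated is 30%, which section 5.a.vi also reports as "the assumed response rate of 30% with dexamethasone alone". Raising the control rate alone is also one-sided: section 5.b quotes 66.7% relapse-free survival with an eltrombopag regimen, and 40% against 66.7% with 53 per arm gives 79.5%.

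**Conclusion.** The point holds in two parts.

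- **Analysis set.** Section 11.c fixes a primary efficacy set that can lose patients in an arm-dependent way in an open-label trial, and it names no all-randomised efficacy analysis. The size of any bias is unknown and probably small.
- **Power.** The 80% in section 11.b does not match the analysis set. With everyone kept, power is about 76% if the assumed rates are completer rates and 15% in each arm become non-achievers independently of outcome. It is about 86% if the rates already count dropouts as failures. The protocol does not say which applies. On the all-randomised set, the same figures assume that the 15% includes never-dosed patients.

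The sample size is not miscalculated, and the 30% control rate is not contradicted elsewhere in the protocol.

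**What to change.** In section 11.c, make ITT (all randomised, as randomised) the primary set for 6mSROT-50. Count any patient without a documented 180-day off-treatment window as not achieved, and keep mITT as a sensitivity analysis.

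In section 11.b, state whether 30% and 56.6% are completer or all-randomised rates, and restate power on the ITT set to match: about 76% under the completer reading with 15% non-evaluable, about 86% under the other.

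The cost is wording in two subsections and, under the completer reading, a less favourable stated power. Sample size, treatment and visits stay as they are.

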 - Definition of 6mSROT-30: platelets higher or equal than 30x10⁹/L in the absence of any ITP treatment including any rescue treatment

for at least 6 consecutive months (≥180 days) from treatment cessation and without WHO grade 2 or more bleeding.

- To evaluate the difference between study arms in the proportion of patients achieving 12mSROT-50 at 12 months (365 days) from treatment cessation.
 - Definition of 12mSROT-50: platelets higher or equal than 50x10⁹/L
 in the absence of any ITP treatment including any rescue treatment
 for at least 12 consecutive months (≥365 days) from treatment
 cessation and without WHO grade 2 or more bleeding.
- To evaluate the difference between study arms in the proportion of patients achieving 12mSROT-30 at 12 months (365 days) from treatment cessation.
 - Definition of 12mSROT-30: platelets higher or equal than 30x10⁹/L in the absence of any ITP treatment including any rescue treatment for at least 12 consecutive months (≥365 days) from treatment cessation and without WHO grade 2 or more bleeding.
- To evaluate the difference between study arms in the proportion of patients with complete response (CR) at 6 months (Day 180), at 12 months (Day 365) from randomisation and End of study Visit (visit 12 months after the last dose of study treatment). We will evaluate this in the total sample and in the absence of any rescue treatment
 - Definition of CR: platelet count ≥100x10⁹/L and absence of bleeding symptoms.
- To evaluate the difference between study arms in the proportion of patients with response (R) at 6 months (Day 180), at 12 months (Day 365) from randomisation and End of study Visit (visit 12 months after the last dose of study treatment). We will evaluate this in the total sample and in the absence of any rescue treatment
 - Definition of R: platelet count between 100x10⁹/L and 30x10⁹/L and at least doubled from baseline and absence of bleeding symptoms.
- To evaluate the difference between study arms in the proportion of patients with global response (GR) at 6 months (Day 180), at 12 months (Day 365) from randomisation and End of study Visit (visit 12 months after the last dose of study treatment). We will evaluate this in the total sample and in the absence of any rescue treatment
 - o Definition of GR: CR or R.

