- To evaluate the difference between study arms in the proportion of patients with response within the target range (TR) at 6 months (Day 180), at 12 months (Day 365) from randomisation and End of study Visit (visit 12

months after the last dose of study treatment). We will evaluate this in the total sample and in the absence of any rescue treatment

- Definition of TR: platelet count between ≥30x10⁹/L and ≤400x10⁹/L.
- To evaluate the difference between study arms in the median time to first response defined as the time from randomization to first response (R) in the absence of any rescue treatment. We will evaluate this in the total sample and in the absence of any rescue treatment.
- To evaluate the difference between study arms in the proportion of patients with early response (ER) and initial response (IR).
 - Definition of ER: proportion of patients with platelet count higher or equal than 30x10⁹/L and at least doble than baseline at first week (Day 7) from randomisation.
 - Definition of IR: proportion of patients with platelet count higher or equal than 30x10⁹/L in the first month (Day 30) from randomisation.
- To compare the difference of means between study arms of the maximum number of consecutive days with platelet response (CR, R, GR and TR) along the study period. We will evaluate them in the total sample and in the absence of any rescue treatment
- To compare the difference of means between study arms of the total number of days with platelet response (CR, R, GR and TR) along the study period. We will evaluate them in the total sample and in the absence of any rescue treatment.
- To evaluate and to compare the proportion of patients who need rescue treatments and proportion and time to treatment failures
- To compare the time to loss of response (LoR) in patients who achieved response in both arms.
 - Definition of LoR: number of days from the first time the patient achieved a platelet count ≥30x10⁹/L until platelet count dropped below 30x10⁹/L measured on 2 occasions with more than 1 day apart or presence of bleeding
- To compare the difference between study arms in the proportion of patients requiring any rescue treatment along the study period.

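### Response R excludes complete response, yet R alone is the event for time to first response and the entry rule for the rITT set; both should use GR (CR or R)

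*Protocol*

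**What the plan says.** Section 6.c of the protocol (repeated in the summary, section 1.j) sets up three response categories, with counts in x10⁹/L:

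- "Definition of R: platelet count between 100x10⁹/L and 30x10⁹/L and at least doubled from baseline and absence of bleeding symptoms"
- "Definition of CR: platelet count ≥100x10⁹/L and absence of bleeding symptoms"
- "Definition of GR: CR or R"

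Section 11.e.i then states: "To compare the time to first response (R) in both arms, Kaplan-Meier method will be used". The censoring rule follows: "Patients who not achieve R will be censored at the date of the last followup". It makes no exception for a patient in CR.

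Section 11.c admits to the rITT population patients who were "randomized and received at least one dose of study medication and achieved response (R) at any time during the study". Section 11.e.i analyses time to loss of response (LoR) in that population. The LoR definition in section 6.c, however, starts the clock at the first count of 30 or more. It sets no upper limit and requires neither doubling nor absence of bleeding at the start.

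Two related definitions sit nearby. Early response (ER, Day 7) needs a count of at least 30 and a doubling from baseline. Initial response (IR, Day 30) has the threshold only: "Definition of IR: proportion of patients with platelet count higher or equal than" 30x10⁹/L.

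**The concern.** GR is defined as the union of CR and R. If R already contained CR, GR would be the same thing as R, so the protocol's own wording makes R a band from 30 to 100 and CR the category above it. A time-to-first-response analysis built on that band does not measure when a patient first responds. It measures when a patient is first seen in the middle range, and it can miss the best responders altogether. The rITT rule carries the same gap into the LoR analysis: the patients most at risk of being left out are those who go straight to a durable CR.

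At stake are the Kaplan-Meier curve and median for time to first response, the log-rank comparison, and the make-up of the LoR population. If one arm produces more direct complete responses, that benefit would show in this analysis as slower or less frequent response.

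**Working it through.** **1. No figure to reproduce.** The protocol states no expected time to first response, no rITT size and no share of direct complete responses. The check is therefore to apply the rules to example patients and then to scale the result under stated assumptions.

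**2. The rules applied to example patients** (baseline 12, no bleeding, counts x10⁹/L):

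| Counts after baseline | First GR | First R | Time to first response | In rITT? | LoR clock starts |
|---|---|---|---|---|---|
| 45, 120, 180 | at 45 | at 45 | event at 45, correct | yes | at 45 |
| 120, 180, then always 100 or more | at 120 | never | censored at last follow-up | no | at 120 |
| 120, 180, months later 80 | at 120 | at 80 | event dated at the fall to 80 | yes | at 120 |

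The second patient has an LoR start date but is outside the LoR population. The third has an LoR clock that starts months before the recorded first response.

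**3. Is a jump past the band plausible?** Counts are weekly at best during the first 8 weeks (section 6.a). Section 5.a.iv reports peaks of 1.3 to 14.9 times baseline after one romiplostim dose. At the top of that range 100 / 14.9 = 6.7, so a baseline of about 7 or more could pass 100. The peak builds over 2 to 3 weeks, so a jump between weekly counts is possible but not certain. For patients enrolled at 30-49 with bleeding (section 7.a), doubling narrows the R band: 2 x 30 = 60 leaves 60-100, and 2 x 49 = 98 leaves 98-100. Many of these patients can respond only as CR.

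**4. Size.** Assumptions: 85% of patients respond (section 5.b gives this for initial effect of high-dose dexamethasone; it is borrowed here as an illustration); a share q of responders goes straight to CR; a share s of those is later seen with a qualifying count of 30-100.

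Wrongly censored = 0.85 x q x (1 - s). Dated late = 0.85 x q x s.

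| q | s = 1 | s = 0.5 | s = 0 |
|---|---|---|---|
| 20% | 0% censored, 17% late | 8.5% censored, 8.5% late | 17% censored |
| 40% | 0% censored, 34% late | 17% censored, 17% late | 34% censored |

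At s = 0 the counted response falls from 85% to 68% (85 - 17) or 51% (85 - 34).

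**5. Effect on the log-rank test.** Simulation with 1,000 runs and 63 patients per arm (section 11.b). Both arms have 85% GR and the same distribution of time to first GR (weekly chance one half, follow-up 52 weeks). A later R falls 2 to 39 weeks after CR, capped at week 52. Two-sided 5% test.

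| Direct CR, DEX / ROM+DEX | s | Rejects using R | Rejects using GR |
|---|---|---|---|
| 20% / 40% | 0 | 48.8% | 5.3% |
| 20% / 40% | 0.5 | 27.7% | 5.8% |
| 20% / 40% | 1 | 17.9% | 5.1% |
| 20% / 20% | 0.5 | 4.5% | 4.6% |

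In the first three rows the rejections are all, or nearly all (17.5 of the 17.9 points in the third), against ROM+DEX, although true response is identical. With s = 0 the expected R events are 63 x 0.85 x 0.80 = 42.8 in DEX and 63 x 0.85 x 0.60 = 32.1 in ROM+DEX. With equal shares there is no distortion of the test.

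**The case against.** A reader might infer that every patient who goes straight to CR is censored and dropped. The protocol does not support that. rITT admits R at any time, and only patients who never show R are censored. Follow-up is long, and romiplostim is tapered, held or stopped under section 9.b, so there are many occasions on which a count between 30 and 100 may be seen. Such patients are events and are in rITT; their error is a late date. Full exclusion falls mainly on durable complete responders, and on any who fall from 100 or more to below 30 between visits.

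A reader might also infer that the test must run against ROM+DEX. That needs different direct-CR shares by arm, and nothing in the protocol establishes a difference. Both arms start with the same dexamethasone course, and section 5.a.iv puts the maximum romiplostim effect at about 10-14 days, so early jumps may be largely shared. The 20% and 40% are assumptions.

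A third inference would be that patients enrolled at 30-49 meet IR at baseline. Section 11.e.i assesses IR at Day 30, so they do not. What stands is narrower: an unchanged count of 30-49 at Day 30 would qualify. For LoR, the wording about first achieving a count of 30 reads more naturally as after treatment, though it does not say so.

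Finally, complete responders remain visible in the CR, GR and TR proportions and durations and in ER, and section 11.e.i labels secondary results exploratory. That lowers the severity. It does not repair an event that omits complete responders, and the endpoint is still tested at p<0.05. Nor is this a detail left to the SAP: the protocol itself fixes the event, the censoring rule and the population.

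**Conclusion.** The point holds in this form: as written, R excludes CR, and using R alone as event and entry rule gives a wrong result for direct complete responders. Those never seen with a qualifying count of 30-100 are censored as non-responders and left out of the LoR analysis. Those who fall into the range later stay in rITT with a first response dated at the fall. The rITT rule also conflicts with the LoR clock.

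The size is unknown from the protocol. Under the assumed 85% response and 20-40% direct CR, wrongly censored patients range from 0% (all later seen at 30-100) to 17-34% (none later seen); the upper figures are bounds, not estimates. Bias in the log-rank test depends on direct-CR shares differing between arms.

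Only secondary analyses declared exploratory are affected. The primary 6mSROT-50 endpoint, its analysis set and the sample size are not. This is a should-fix.

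**What to change.** - Make GR (CR or R) the event for time to first response, and censor only patients who never reach GR.
- Make GR at any time the entry rule for rITT.
- Start the LoR clock at the first GR after randomisation, so that population and time origin agree.
- Keep R alone as a descriptive category.
- Lesser point: consider adding the doubling requirement to IR, in line with ER. This is a separate choice and the main correction does not depend on it.

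The edits must be made consistently in the summary (sections 1.g and 1.j), the objectives (5.c), the endpoints (6.c), the populations (11.c) and the analysis text (11.e.i). That is more than one place, but each change is short. Platelet counts and bleeding are already recorded at every visit, so no new data are needed. The change can be made before database lock, without reference to results, and carried into the SAP.
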